 - 3) that we will have to obtain HIPPA consent, since this consent is what allows us to look at their child's medical and insurance records.
13. Ask if they will sign consent form 1.

HIPPA Consent:

1. Acknowledge they are likely familiar with HIPPA due to previous trips to the doctor/hospital.
2. Their signature is needed because it allows us to receive and share information with other HIPPA covered entities.
3. Point out below differences with giving us HIPPA consent versus other times they typically encounter HIPPA:
 - Although they can withdraw from the study at any time by calling, that to withdraw HIPPA authorization requires notification in writing by email or letter, because it involves medical records, etc. The phone number and email address are at the top of the consent forms.
 - Because of the role of NIH and the IRB they can audit the project and that during this audit they may look at their child's research records. This look may reveal some of their child's medical/insurance information or they may ask to see this information to clarify a question. They are not HIPPA covered entities, but we expect them to treat the information in the same manner as HIPPA entities. Records chosen for an audit are random, and that their child's record may or may not be selected.
 - If they give HIPPA authorization to others, after this project, and there is project information in their child's medical record, that these others will have the project information (unless they restrict access)
4. Offer to let parent read HIPPA consent on the screen

Informed consent 2:

1. GS testing is not a new test, but we are trying to determine if having the test sooner rather than later in the process of learning a reason for why their child came to clinic today, impacts care they receive down the road. For example, if they have more or less additional test than children who do not have GS testing.
2. Test results typically come back into one of three categories:
 - Positive, meaning the change we see is the cause for why their child came to clinic today.
 - Uncertain, means that there is not enough data yet to know if the change we see causes health issues or is part of the many changes that people just have.
 - Negative, means at this time we did not find a change that is related to why their child came to clinic today.

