Appendix XXV. CLIA Lab Tracking in NCGENES 2 Genomic Molecular Workbench (GMW)

NCGENES2 Protocol for Tracking of Clinical Laboratory Samples, Sequencing Confirmation, and Reports

Version 1.0

[figure not shown]
Overview

Participants who are randomized to and consent to having genomic sequencing performed as part of the NCGENES2 project will provide paired samples: one to undergo genomic sequencing through the research lab, and a second which will be received in a clinical laboratory (monitored under CLIA). The clinical laboratory will receive and extract DNA from the sample, perform genotyping of a set of polymorphic single-nucleotide variants (the "identity-check" SNVs) and hold extracted DNA until confirmation of research results (pathogenic, likely pathogenic, or reportable variant of uncertain significance) is requested by the molecular sign-out committee. After attempt at confirmation, the clinical laboratorian will indicate whether this confirmation was successful. If confirmation was successful, then the clinical lab director will prepare a clinical report to be included in the participant's medical record, and will also record the report text as part of the study data set.

System of record

The system of record for these activities within the NCGENES2 project is the **NCGENES2 Genomic Molecular Workbench (GMW)**, located at <https://ncg2.unc.edu> with authentication using a UNC onyen (<https://onyen.unc.edu>). Access to this system is restricted to computers on the UNC School of Medicine network or through the UNC Campus VPN. Authorization to access this system is controlled by study coordinators.

Upon login to this system, the user is presented with a role-based list of pending tasks that can be performed (Figure 1)

The screenshot shows the 'GMW Workflow Manager' interface. The left sidebar contains a navigation menu with items: Main Dashboard, Wet Lab Dashboard, Administration, Participants, Research Lab, Clinical Lab, Molecular Analysis, Log Out, UNC Health Care, UNC School of Medicine, and UNC. The main content area is titled 'Main Dashboard' and contains a 'Your Workflows' section. This section includes a 'Workflow Step Status Filter' dropdown set to 'No filter', a button to 'Show All Workflows' (which is set to 'No'), and a table of pending workflows. The table has columns: Participant, Workflow, Workflow Step, Status, Role, and Details. It shows two rows:

Participant	Workflow	Workflow Step	Status	Role	Details

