After a specimen has been accessioned into the system, the next pending task related to this specimen for the CLIA Laboratorian is "UNC CLIA Save Genotypes" or "Mission CLIA Save Genotypes" for the respective laboratories (for example, as seen for participant TEST_00001 in Figure 1).. Clicking on the text of this pending workflow step will display the interface (Figure 3) for entry of genotypes of these "identity check" polymorphisms. Genotypes for each polymorphism (indicated by dbSNP RS identifier) are entered using a drop-down box of options.

GMW Workflow Manager

Main Dashboard

Wet Lab Dashboard

Administration

Participants

Research Lab

Clinical Lab

Molecular Analysis

Log Out

UNC Health Care

UNC School of Medicine

UNC

UNC CLIA Blood Specimen Check-In - UNC CLIA Save Genotypes TEST_00001

RSID	CLIA Genotypes
rs600859:	A/A (A)
rs1800351:	A/C (M)
rs3746438:	C/G (S)
rs2236181:	A/C (M)
rs11734372:	A/T (W)
rs2229992:	A/C (M)
rs10835051:	missing (X)
rs12129650:	A/G (R)

Submit

Upload a Sequencer Data Output Text File

File Name

Choose File No file chosen

Upload a sequencer file

Upload

FIGURE 3: INTERFACE FOR RECORDING SANGER GENOTYPING OF "IDENTITY CHECK" GENOTYPES

Requests for confirmation of genomic sequencing results

Variants which are identified as reportable by the molecular sign-out committee (Pathogenic, Likely pathogenic, or reportable Variants of Uncertain Significance) will be marked by the committee within the GMW. This creates a notification to individuals with the "CLIA Laboratorian" role, and also adds the relevant task ("CLIA Variant Analysis Results") to their dashboard.

Primer design

Selecting "Clinical Lab" and then "Unresolved variant confirmation" from the menu to the left provides a list of all variants for which CLIA confirmation is pending. This list includes a column for amplicon design. The laboratorian will click in this column to obtain the sequence surrounding the variant to be confirmed as well as suggested PCR primers.

Recording of variant confirmation

The results of variant confirmation are recorded in the workflow step for "CLIA Variant Analysis Results". These are recorded in the column labeled "Confirmed" using one of the following codes:

- P: Pending (used for variants for which confirmation has not been attempted, so will not be a final code)

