- U: Unknown- unable to demonstrate presence or absence of the variant (e.g., unable to design primers to amplify the relevant region, or unable to define primers that differentiate between this region and paralogous sequence)
- N: No, not confirmed- Sanger sequencing indicates that the variant is not present
- Y: Yes, confirmed- Sanger sequencing indicates that the variant is present.

When all of the variants have been assigned to one of the final categories (U, N or Y), the laboratorian presses the submission button to send the results on to the molecular pathologist for final interpretation.

Molecular pathologist determination of final result and reporting

After Sanger sequencing of the requested variants is performed, the molecular lab director determines the final case-level result. This includes marking whether the variants requested by the sign-out committee were confirmed, and if so, the generation of the text of the report. When no reportable findings are identified in the research lab (or none of the requested findings are confirmed in the clinical lab) then a negative report is generated directly by the GMW. When there are

findings to report that do confirm, then the laboratory director prepares a report according to their usual clinical practice. In addition, the laboratory director provides, within the GMW, the text of the clinical report (without any identifiable information) and the classification of the case-level result which can include one or more of the following categories:

- Definitive positive:
 - One or more Pathogenic variants in a gene, phenotype consistent with condition, with known phase or *de novo* inheritance consistent with expected inheritance pattern
- Probable positive:
 - One or more Likely Pathogenic variants in a gene, phenotype consistent with condition, with known phase or *de novo* inheritance consistent with expected inheritance pattern
- Inconclusive - due to unknown phase:
 - At least two Pathogenic/Likely Pathogenic variants in AR condition or X-linked recessive condition in female with phase not determined
- Inconclusive - due to variant uncertainty:
 - Case that would otherwise meet Definitive Positive or Probable Positive but at least one of the involved variants is a VUS
- Inconclusive - due to insufficient zygosity:
 - Single Pathogenic or Likely Pathogenic variant identified in AR condition or in female with X-linked condition
- Inconclusive - phenotype mismatch:

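### A case whose reportable variant could be neither confirmed nor excluded (code U) gets the same automatic negative report as one shown absent, and no result category fits it

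*Protocol*

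**What the plan says.** All the rules at issue are in Appendix XXV of the protocol unless stated otherwise.

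- **What goes to confirmation.** The clinical laboratory is asked to confirm "Variants which are identified as reportable by the molecular sign-out committee (Pathogenic, Likely pathogenic, or reportable Variants of Uncertain Significance").
- **The codes.** Apart from a pending code, there are three outcomes. Y means the variant is present. The other two are "N: No, not confirmed- Sanger sequencing indicates that the variant is not present" and "U: Unknown- unable to demonstrate presence or absence of the variant". The examples given for U are technical: no primers can be designed for the region, or none that distinguish it from paralogous sequence.
- **U is final.** The case moves on "When all of the variants have been assigned to one of the final categories (U, N or Y").
- **Human step.** Results then go for interpretation, and "the molecular lab director determines the final case-level result".
- **Reporting rule.** With no reportable research finding, or when "none of the requested findings are confirmed in the clinical lab) then a negative report is generated directly by the GMW". The appendix's overview states the other branch: "If confirmation was successful, then the clinical lab director will prepare a clinical report".
- **Case-level categories.** Two positive classes, five inconclusive classes (unknown phase, variant of uncertain significance, insufficient zygosity, phenotype mismatch, novel gene) and Negative.

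Elsewhere, the section on results for sequenced participants equates negative with no variant being judged clinically significant. The overview of the biospecimen protocol lists the states a physician can see: pending, negative, or a positive or uncertain result that has been CLIA confirmed. In the consent talking points of Appendix IV, families are told: "Negative, means at this time we did not find a change that is related to why their child came to clinic today".

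**The concern.** The protocol draws a distinction at variant level and discards it one step later. N is evidence of absence, and U is absence of evidence. A rule that depends on whether anything was confirmed treats both as not Y. A variant that the sign-out committee called reportable, and that the laboratory could not test, therefore leads to the report meant for a child with nothing to report.

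Two things are at stake. One is the result returned to the physician and family of that child. The other is the case-level field in the study data: the list has no value for an untestable finding, so Negative is the only one whose reporting path leads there.

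**Working it through.** No figure in the protocol needs reproducing. The check traces the rule over the final codes and compares the output with the rest of the text.

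**Step 1: trace the rule as written.**

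| Final codes in the case | Output |
|---|---|
| no reportable research finding | automatic negative |
| Y, alone or with others | report prepared by the director |
| N, or N and N | automatic negative |
| U, or U and U | automatic negative |
| N and U | automatic negative |

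Every case with at least one U and no Y has the same output as a case in which Sanger showed all variants absent.

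**Step 2: look for a category that fits.** Four of the five inconclusive classes describe phase, zygosity, phenotype fit or gene validity. The fifth, variant uncertainty, is tied to a variant's classification as of uncertain significance and not to failure of the confirmatory assay. A pathogenic variant coded U meets none of them on that account. The physician-facing list has no place for it either, because its non-negative states are labelled as CLIA confirmed. The consent script's uncertain result concerns a variant whose health effect is unknown, which is a different matter.

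**Step 3: compare with the protocol's meaning of negative.** By construction, a U variant was marked reportable by the sign-out committee, so the case does not meet the return-of-results description of a negative. Where the U variant is a primary finding, the meaning given to families at consent does not describe the case either: a change was identified and could not be tested.

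**Step 4: test the alternative reading.** The N label contains the words not confirmed, so one could read the rule as covering N only. U cases then have no reporting rule at all, and the gap remains in another form.

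**Step 5: scale.** Planned enrollment is 850 (note in the overview of interventions) and allocation is 1:1 (Appendix III), so at most 850 / 2 = 425 children are in the sequencing arm. The protocol gives neither the share sent for confirmation nor the share ending in U. Assumptions, for illustration only: 20–40% sent for confirmation, and 1–5% of those ending with U and no Y.

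- Low: 425 × 0.20 × 0.01 = 0.85, about 1 child (0.2% of the arm).
- High: 425 × 0.40 × 0.05 = 8.5, about 9 children (2.0% of the arm).

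**The case against.** The best defence is that a person decides first. Every completed case goes to the molecular pathologist, and the director sets the case-level result, including whether the requested variants were confirmed. A competent director may well stop a U-only case from going out as a plain negative. This stands as mitigation. It does not close the gap, because the same paragraph has the system generate the negative report directly and gives the director neither an instruction nor a category for U.

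It is also fair to say that requiring confirmation before a positive or uncertain result enters the medical record is deliberate and consistent throughout the protocol. That is not challenged here. Withholding an unconfirmed finding from the record differs from labelling the case negative.

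Four stronger inferences are tempting and not supported:

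- **Diagnostic yield is understated and the negative group contaminated.** The protocol shows no yield analysis, the SAP is not at hand, and U is recorded per variant, so these cases can be identified in the data.
- **A recessive case with one Y and one U must be classed as insufficient zygosity.** That class refers to a single variant having been identified, and the text does not say how an unconfirmed second variant counts.
- **The report sent to the family is untrue.** Its wording is not in the document. The consent line is a talking point, and the script adds that a negative result could change with more research.
- **The randomised comparison is biased.** Appendix III states an intention-to-treat analysis, and membership of an arm does not depend on the case-level label.

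**Conclusion.** The point holds in a limited form. As written, the protocol routes cases with U and no Y to the same automatic negative report as cases shown absent. It offers no case-level class or physician-facing state for them, and so conflicts with its own description of a negative result. This is a stated rule that misclassifies, not a detail left to another document.

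The size is unknown. The 1 to 9 children shown above rest wholly on assumed rates, and 425 is a ceiling because some families leave before the second randomization or decline sequencing. Any effect on aggregate results is likely to be small. The reason to act is that each such child's result is misdescribed and the correction is cheap. The conclusion assumes that the director does not intervene under an unwritten practice. If such a practice exists, it should be written down.

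**What to change.** 1. In the rule for the automatic negative, separate U from N, so that a case with U and no Y no longer meets the condition merely because nothing was confirmed.
2. Add a case-level class for findings that could be neither confirmed nor excluded, assigned by the laboratory director and recorded apart from Negative.
3. Query the workbench for cases already submitted with at least one U and no Y, and review how each was classified and reported.
4. Reconcile the U code, the automatic-negative rule, the case-level categories, the states shown to physicians and the wording given to families. What is clinically reported for such a finding is for the sponsor to decide.

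The cost is one changed condition, one added category, one database query with review of the cases it returns, and aligned text. No new participants, samples or procedures are needed.

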Remaining DNA can be used for future research with parental consent and in rare cases with required concordant child assent (which is obtained at the time of GS randomization consent/assent). DNA will be stored indefinitely, but linked data will be destroyed on the patient's 18th birthday rendering all remaining samples anonymized.

In some cases, the physician may determine that parental DNA confirmatory testing is needed to interpret the genomic sequencing results of the child. In this case, the genetic counselor or nurse notifies the family and the research team of the need to collect parental DNA. The research team contacts the patient's parent to let them know that parental/relative genetic testing consents and saliva kits are being mailed (one for each parent). The research study coordinator will wait approximately one week and phone the parents to consent them by phone, have them sign the consents and return them along with their saliva samples to the BSP lab in an addressed/postage paid envelope. Extra consents will be provided so that the parents may keep copy for their records. In rare cases other adult relatives may need to be tested. This will be determined by the ordering physician. NCGENES 2 will pay for additional confirmatory testing in the CLIA if the physician determines that it is necessary for the interpretation of the results for the child.

FIGURE 1. Overview of sample flow through study laboratories, molecular sign-out, CLIA confirmation, and reporting

Collecting Blood Samples at Visit 1

NCGENES 2 prioritizes collection of blood for research biospecimens. As often as possible, NCGENES 2 blood specimens will be collected immediately following Visit 1 from participants consented to exome sequencing. This section outlines the protocol for collecting blood samples at each NCGENES 2 site.

Pre-Visit 1: Preparation of the Blood Collection Kit

All sites will use a generally uniform procedure for preparing blood collection kits. A blood kit is created for each participant and clipped to that participant's folder for use in the clinic (see "[Preparation for Visit 1](#)" on page 22). In addition, a second blood kit (without forms) should always be brought to the clinic should a redraw become immediately necessary due to failed collection.

Kit contents

Each blood collection kit will include:

- 2 biohazard bags
- 2 purple top 3ml EDTA vacutainers (**ALWAYS CHECK EXPIRATION DATE**)
- 5 ID barcode labels (includes 1-2 extra)

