 - Case that would otherwise meet Definitive Positive or Probable Positive but where the condition would not explain all of the patient's phenotype, where the patient does not exhibit all characteristics expected of the condition, or where there is discordant co-segregation of phenotype with the variant within a pedigree (e.g., implicating incomplete penetrance or phenocopy)
- Inconclusive - novel gene:
 - Case where the association of the implicated gene with the patient's phenotype has not been definitively established
- Negative

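### The case-level result categories in Appendix XXV treat X-linked conditions in girls inconsistently and, read strictly, leave no category for a single dominant or hemizygous variant of unknown parental origin

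*Protocol*

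**What the plan says.** Appendix XXV, in the part on the molecular pathologist's final result, lists the categories that the laboratory director enters in the Genomic Molecular Workbench. More than one may be entered for a case.

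- The definitive-positive rule reads: "One or more Pathogenic variants in a gene, phenotype consistent with condition, with known phase or *de novo* inheritance consistent with expected inheritance pattern".
- The probable-positive rule is the same test with a lower variant class, beginning "One or more Likely Pathogenic variants in a gene, phenotype consistent with condition".
- Inconclusive, unknown phase: "At least two Pathogenic/Likely Pathogenic variants in AR condition or X-linked recessive condition in female with phase not determined".
- Inconclusive, variant uncertainty: "Case that would otherwise meet Definitive Positive or Probable Positive but at least one of the involved variants is a VUS".
- Inconclusive, insufficient zygosity: "Single Pathogenic or Likely Pathogenic variant identified in AR condition or in female with X-linked condition".
- Inconclusive, phenotype mismatch: a case otherwise positive in which the condition and the child's features do not fully match, or in which variant and phenotype do not travel together in the family.
- Inconclusive, novel gene: "Case where the association of the implicated gene with the patient's phenotype has not been definitively established".
- Negative. The same part has the system issue a negative report when nothing reportable was found or nothing was confirmed.

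On parental samples, the overview of the Biospecimen Protocol says: "In some cases, the physician may determine that parental DNA confirmatory testing is needed to interpret the genomic sequencing results of the child". The family-study request form in Appendix XXXVIII lists determining phase and determining de novo or inherited origin as two separate reasons for testing a relative.

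**The concern.** Two features of this list do not fit together.

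First, the unknown-phase category speaks of X-linked recessive conditions in girls, while the zygosity category speaks of X-linked conditions in girls without that restriction. One copy of a P/LP variant is sufficient in an X-linked dominant condition, so calling such a result inconclusive for want of a second copy is a wrong code by the category's own name.

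Second, the positive categories are open to a single variant but ask for phase or de novo origin. Phase is a relation between two variants, and de novo origin can be shown only with parental DNA, which is not collected routinely.

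At stake is the consistency of the recorded result. The Workbench is the system of record for these activities. If the same finding can be entered as positive, inconclusive or neither depending on the reader, or on whether a physician asked for parental samples, anything later tabulated from these codes inherits that variation.

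**Working it through.** No stated sample size, power or yield bears on this point, so there is no plan figure to reproduce. The check is to apply the category definitions to typical cases under two readings:

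- Strict: known phase or de novo origin must actually be shown.
- Lenient: phase counts as satisfied when there is only one variant.

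All cases assume a matching phenotype and an established gene.

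| Case | Strict | Lenient |
|---|---|---|
| Dominant, one P, parents untested | none | Definitive |
| Dominant, one LP, parents untested | none | Probable |
| Dominant, one P, shown de novo | Definitive | Definitive |
| Dominant, one P, shown inherited | none | Definitive |
| Hemizygous boy, one P, mother untested | none | Definitive |
| X-linked dominant, girl, one P, de novo | Definitive and zygosity | Definitive and zygosity |
| X-linked dominant, girl, one P, parents untested | zygosity | Definitive and zygosity |
| X-linked dominant, girl, one VUS, de novo | variant uncertainty | variant uncertainty |
| Recessive, two P, known to be on opposite copies | Definitive | Definitive |
| Recessive, two P, phase unknown | unknown phase | unknown phase |

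**Why the dominant case with untested parents has no home on the strict reading.** It is not positive, because neither phase nor de novo origin is shown. It is not unknown phase, which needs two variants in a recessive condition. It is not zygosity, which is limited to autosomal recessive conditions and girls with X-linked conditions. It involves no VUS, no mismatch and no novel gene. It is not Negative, because a reportable finding was confirmed.

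**Knock-on.** Variant uncertainty and phenotype mismatch are both defined by reference to the positive categories. On the strict reading a single dominant VUS with untested parents therefore drops out too.

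**X-linked dominant, girl.** The zygosity code applies under both readings. When the variant is de novo she also meets a positive category under both. Multiple codes are allowed, but no order of precedence is given.

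**Effect of correcting the zygosity category alone.** The de novo girl moves from two codes to Definitive only. The girl with untested parents moves from inconclusive to no category on the strict reading. The two defects therefore have to be corrected together.

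**Size.** The number of affected cases is the product of:

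- children sequenced;
- the share with a P/LP explanation;
- the share of those with a single dominant, hemizygous or X-linked dominant variant;
- the share affected by the wording (origin not established and read strictly, or X-linked dominant in a girl).

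Only the first can be bounded from the protocol. With 1:1 allocation it is at most 850 / 2 = 425, or 800 / 2 = 400 using the number in the overview diagram. No value is given for any of the other three, so the product cannot be computed.

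**The case against.** The strongest objection is that the gap exists only on the strictest reading. The positive categories say one or more variants, so single-variant cases were expected. With one variant, phase is not in question, and the closing test is agreement with the expected inheritance pattern. The phenotype-mismatch category also treats discordant co-segregation within a family as a reason to downgrade a case that would otherwise be positive, which suggests that inherited variants can be positive. Asking for de novo evidence before a definitive label may also be deliberate caution. This stands in part: the gap is a matter of reading. But the lenient reading is nowhere written down, and the request form in Appendix XXXVIII treats phase and de novo origin as separate questions.

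For the X-linked point, one can say that the category's title gives a director reason not to use it where one copy suffices, and that codes are not exclusive. Neither removes the conflict in wording, and the double code remains even on the lenient reading.

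A reader might go further and infer that every single variant in a girl with an X-linked condition is called inconclusive. That is too broad: the rule covers only P/LP variants, and a de novo VUS goes to variant uncertainty.

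**Conclusion.** The definitions are inconsistent on X-linked recessive versus X-linked, and this holds on either reading. A girl with one P/LP variant in an X-linked dominant condition is coded inconclusive, and both inconclusive and positive if the variant is de novo, with no precedence rule. On a strict reading the definitions are also not exhaustive, because a single dominant or hemizygous P/LP variant of unknown parental origin has no category. That second part depends on how a director reads the clause. The supported consequence is that such cases can be coded inconsistently.

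It is tempting to conclude that the diagnostic yield of sequencing is misclassified by some number of percentage points. The protocol does not support that. It defines no yield endpoint and no mapping from these codes to a yield; a statistical analysis plan, not available here, may set one. Any such figure would rest wholly on assumed rates, and its lower bound is near zero if directors read the clause leniently or parents are tested. A later plan could decide how codes are grouped, but it could not make codes assigned on different readings comparable without re-coding.

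**What to change.** Make these changes to Appendix XXV in one edit:

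1. Limit the insufficient-zygosity category to autosomal recessive conditions and, in girls, X-linked recessive conditions, matching the unknown-phase category.
2. Reword Definitive and Probable positive so that the phase requirement applies only where the condition needs two variants.
3. State which category holds a single dominant-acting or hemizygous P/LP variant of unknown parental origin. The choice of category belongs to the laboratory directors; what matters is that it is written down.
4. Record parental origin (de novo, inherited, unknown) in a separate field, so that parental testing done later updates that field visibly.

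Then re-check any cases of these types already coded, using the stored variant data.

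The cost is a wording change, one added field and a small re-review of coded cases. No new testing is needed.
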